3.7. Data collection

Clinical data will be collected at certain time points of this study. The requirements to data collection and study visit schedule are given in table 1.

Table 1: Study stages and procedures

Stages / Procedures	Screening	Distribution into groups and surgery	Postoperative period (early observation: 24-48 hours)	Before discharge (ca. after 21 days)	6 months post operation ± 14 days	12 months post operation ± 30 days
	Visit No. 1	Visit No. 2	Visit No. 3	Visit No. 4	Visit No. 5	Visit No. 6
Informed consent	X					
Anamnesis morbi	X					
Physical examination, evaluation of orthopedic, somatic and neurological status	X	X	X	X	X	X
Evaluation of quality of life (GMFCS, RLAS, FIM, MACS)	X				X	X
X-ray ¹	X			X	X	X
Intraoperative control efficacy evaluation		X				

CHILDren with neuromuscular diseases – efficacy eVALuation of spinal deformity surgeRY via different pedicle screw fixation systems study
CHIVALRY study

Clinical blood analysis ²	X		X	X		X*
Biochemical blood analysis ³	X		X			X*
Spirometry*	X					X*
EchoCG*	X					X
CT ⁴	X			X		X**
MRI ⁵	X					
Documentation of serious adverse events		X	X	X	X	X

1. Spinal X-ray (from Th1 to S4), 2 standard projections.
2. RBC, hematocrit, hemoglobin, WBC, thrombocytes, ESR.
3. Total protein, creatinine, urea, bilirubin, AST/ALT, glucose.
4. Spine CT (from Th1 to S4).
5. MRI of the spine and the spinal cord.

* Performing research only for medical reasons;

** If there are signs of a bone block in the area of instrumental fixation according to the radiograph of the spine

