3.8.2. Enrollment of patients in the study and screening

A patient is considered a study participant only after informed consent forms have been signed by a patient and their parents.

The screening visit (visit No. 1) consists of the following procedures:

- patient history;
- physical examination and clinical evaluation: physical status (body mass index);
- functional status and life quality (with VAS, FIM, MACS, GMFCS);
- Spine X-ray: scoliotic and kyphotic deformity measurements (Cobb angle), static and dynamic imbalance in frontal and sagittal planes;
- laboratory tests: clinical blood analysis, blood chemistry;
- spirometry, ECG, echocardiography;
- spine CT with the assessment of structural vertebral changes;
- MRI of the spine and spinal cord.

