3.8.5. Visit No. 4. Before discharge (ca. after 21 days)

The duration of inpatient stay is determined by standards of the healthcare institution and on the average amounts to 21 days (depending on the patient's clinical condition). The following study procedures will be performed before discharge:

- Physical examination;
- Spine X-ray: scoliotic and kyphotic deformity measurements (Cobb angle), static and dynamic imbalance in frontal and sagittal planes;
- Spine CT and verification of screw position;
- laboratory tests (clinical blood analysis, blood chemistry);
- documentation of serious adverse events.

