3.8.7. Visit No. 6. 12 months after the procedure

The following study procedures will be performed during a scheduled visit 12 months after the procedure:

- physical examination and clinical evaluation: physical status (body mass index);
- functional status and life quality (with VAS, FIM, MACS, GMFCS);
- spine X-ray: scoliotic and kyphotic deformity measurements (Cobb angle), static and dynamic imbalance in frontal and sagittal planes;
- laboratory tests (clinical blood analysis) (as an option if there is a medical condition);
- spirometry, ECG, echocardiography (as an option if there is a medical condition);
- Spine CT with evaluation of screw position and fusion mass (as an option, if there are signs of a bone block in the area of instrumental fixation according to radiographs of the spine);
- documentation of serious adverse events.

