6. STATISTICAL ANALYSIS AND METHODS

Primary and additional quantitative efficacy and safety criteria will be summarized in shift tables and presented by means of descriptive statistics; the appropriate methods will be selected depending on the data. Missing data will be indicated as N/A and not considered in aggregate statistics. The significance of differences between data groups will be evaluated using the criteria depending on the number of observations and distribution type of parameter values within groups. Software: Statistical Package for the Social Sciences (SPSS), v. 22.0 (SPSS Inc., Chicago, IL, USA). T-criteria: 1) comparison of correction of sagittal and frontal spinal deformity components with graded FC parameters. Differences will be considered significant if two-sided $p < 0.05$.

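### Table 1 and the visit lists contradict each other on ECG, EchoCG and blood chemistry, and section 6 has no rule for 12-month blood and cardiac results obtained only for cause

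*Combined protocol and SAP*

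**What the plan says.** Section 3.7 gives Table 1 its authority: "The requirements to data collection and study visit schedule are given in table 1". Its single-asterisk footnote is "Performing research only for medical reasons". The relevant Table 1 rows are:

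- "Clinical blood analysis ²": marked at Visits 1, 3 and 4, and starred at Visit 6.
- "Biochemical blood analysis ³": marked at Visits 1 and 3, blank at Visit 4, and starred at Visit 6.
- EchoCG: asterisk on the row label, plain marks at Visits 1 and 6.
- Spirometry: asterisk on the row label, plain mark at Visit 1, starred mark at Visit 6.
- ECG: no row.

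The visit lists read differently. At screening, 3.8.2 has "spirometry, ECG, echocardiography" with no condition attached. Before discharge, 3.8.5 has "laboratory tests (clinical blood analysis, blood chemistry". At 12 months, 3.8.7 has "laboratory tests (clinical blood analysis) (as an option if there is a medical condition" and does not mention blood chemistry. It also lists spirometry, ECG and echocardiography there as optional, on the same medical condition.

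On analysis, section 6 states: "Primary and additional quantitative efficacy and safety criteria will be summarized in shift tables". It adds descriptive statistics, shows missing values as N/A and leaves them out of aggregates. It names no laboratory or cardiac test. Section 3.2 makes none of these tests an endpoint, although the primary endpoint needs lung parameters at 12 months.

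**The concern.** There are two linked problems.

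The first is that two schedules in one protocol give different requirements for the same visit. Whether a patient has an ECG recorded, an EchoCG at screening or chemistry before discharge would depend on the page that staff follow. The safety data would then be incomplete in a way that cannot be told apart from protocol deviation.

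The second is selective measurement. A test done at 12 months only when there is a medical reason is observed in patients who differ systematically from the rest. Leaving the untested patients out of aggregates, as section 6 does, treats the tested ones as if they stood for the cohort. Section 6 has no separate rule for for-cause results.

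**Working it through.** **Step 1: schedule against schedule.** The plan states no figure to reproduce, so the check sets each Table 1 cell beside the matching visit list.

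| Test | Visit | Table 1 | Visit list | Agree? |
|---|---|---|---|---|
| ECG | 1 | no row | listed, unconditional (3.8.2) | No |
| ECG | 6 | no row | listed, optional (3.8.7) | No |
| Chemistry | 1 | marked | listed (3.8.2) | Yes |
| Chemistry | 3 | marked | listed (3.8.4) | Yes |
| Chemistry | 4 | blank | listed (3.8.5) | No |
| Chemistry | 6 | starred | not listed (3.8.7) | No |
| EchoCG | 1 | plain mark, starred label | listed, unconditional (3.8.2) | Depends on asterisk |
| EchoCG | 6 | plain mark, starred label | listed, optional (3.8.7) | Depends on asterisk |

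The ECG and chemistry conflicts do not depend on any asterisk: a row is absent, a cell is blank, and a test is not listed.

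**Step 2: EchoCG under each reading of the label asterisk.**
- If it governs the whole row, EchoCG is for-cause at screening in Table 1 but unconditional in 3.8.2: conflict at Visit 1.
- If it does not, EchoCG is required at 12 months in Table 1 but optional in 3.8.7: conflict at Visit 6.

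One conflict remains either way; only its location changes. Under the first reading, screening spirometry conflicts with 3.8.2 as well. The table was read from a PDF, so the asterisk's position should be checked against the original.

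**Step 3: what section 6 would do with for-cause results.** Clinical blood analysis at 12 months is for-cause in both sources. Chemistry is for-cause in Table 1. ECG and echocardiography are for-cause in 3.8.7. If these count as safety criteria:
- Descriptive statistics by visit would set a broad baseline group against a selected 12-month group. For the blood tests the baseline group is everyone, since both sources require them at screening. For EchoCG that is not certain (Step 2).
- A shift table cross-classifies the same patients at two visits, so untested patients leave both margins. It compares like with like, but only within the selected subset.

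**Step 4: an illustration of direction, not an estimate.** The documents do not say what share would be tested for cause. Assume a standardised marker (lower is worse), no true change, and testing at 12 months of only the least well fraction q. Let c be the correlation of being unwell with the 12-month value, and rho the correlation between visits. With phi the standard normal density and z_q the cut-off for fraction q:

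- by-visit bias = -c × phi(z_q)/q
- paired bias = (1 - rho) × by-visit bias

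With c = 0.5:

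| q | Tested, of 70 | By-visit | Paired, rho 0.5 | Paired, rho 0.8 |
|---|---|---|---|---|
| 0.2 | 14 | -0.70 SD | -0.35 SD | -0.14 SD |
| 0.5 | 35 | -0.40 SD | -0.20 SD | -0.08 SD |
| 1.0 | 70 | 0 | 0 | 0 |

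For q = 0.2: phi(z_q)/q = 0.280/0.2 = 1.40; 0.5 × 1.40 = 0.70; then 0.5 × 0.70 = 0.35 and 0.2 × 0.70 = 0.14. Over q from 0.1 to 0.8 and c from 0.3 to 0.8, the by-visit bias runs from -1.40 to -0.10 SD, and the paired bias (rho 0.5 or 0.8) from -0.70 to -0.02 SD. Every input except the 70 is assumed. The width of the range shows that the size cannot be derived from the plan.

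**The case against.** The strongest reply is that this is a tidying matter. The trial has one centre, which is also the sponsor. Section 3.8 says that procedures follow current standards of care and allows unlisted examinations at the physician's discretion. That largely disposes of the 12-month chemistry mismatch, since a for-cause test may be done whether or not it is listed. It also means that a missing ECG row does not show that patients would go to surgery without an ECG. A reader might add that section 1.1 makes cardiopulmonary failure the main risk here. What it does is cite autopsy diagnoses in order to name decompensated spine deformity as the main reason for premature death. These arguments limit the clinical harm. They do not make the two schedules agree.

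The EchoCG row can also be defended as ambiguous. The spirometry row repeats the asterisk on its Visit 6 cell, which would be redundant if the label already covered the row. That is fair, but Step 2 shows a conflict under both readings.

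On the analysis, three stronger readings are tempting and the documents do not support them:

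- A reader might infer that section 6 commits to shift tables of blood tests and EchoCG. It refers to safety criteria without naming any test, and the only safety outcome the protocol defines is the serious adverse event (section 5). Inclusion is plausible, because safety is an objective and these are scheduled measures with a baseline, but it is not stated.
- A reader might infer that a shift table would compare everyone at baseline with only the unwell at 12 months. That mismatch belongs to by-visit descriptive statistics. A shift table pairs the same patients; its fault is that it represents only the selected subset.
- A reader might put a rate on the distortion. If 10-30% are tested for cause, 30-50% of those are abnormal and 5% of the rest would be, the true share runs from 0.10 × 0.30 + 0.90 × 0.05 = 7.5% to 0.30 × 0.50 + 0.70 × 0.05 = 18.5%, against 30-50% among those tested. All three inputs are assumed, the 30-50% is an input restated, and the comparison says nothing about change from baseline.

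**Conclusion.** The schedule contradiction holds. Three conflicts are firm: ECG without a table row, chemistry at Visit 4, and chemistry at Visit 6. A fourth, on EchoCG, exists under either reading of the asterisk, and its location needs checking in the original document.

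The analysis point holds conditionally. If blood tests, ECG or EchoCG are treated as safety criteria, the rule of dropping missing values makes any 12-month aggregate describe only patients tested for a medical reason. Under the assumptions in Step 4 this makes patients look worse at 12 months, more so in by-visit summaries than in paired ones. No figure can be given from the documents.

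Because none of these tests is an endpoint, the point bears on safety reporting and not on the primary conclusion. It should be corrected, and the correction is cheap. The same footnote also makes 12-month spirometry for-cause. That touches the primary endpoint and is a separate, more serious matter.

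**What to change.** 1. Reconcile Table 1 with 3.8.2, 3.8.5 and 3.8.7 so that ECG, EchoCG and blood chemistry each have one stated requirement at each visit. Place the asterisk on the cells it governs, and settle in the same way whether it covers screening spirometry. Which version applies is for the clinical team.
2. In section 6, name the tests that count as safety criteria. State that for-cause 12-month blood, ECG and EchoCG results will be given as a listing, with the number tested and the reason, and will not be pooled into by-visit summaries or shift tables.
3. Do not extend that restriction to spirometry. A general rule limiting shift tables to tests scheduled for everyone would remove the 12-month lung data that the primary endpoint needs. That gap has to be dealt with separately.

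The cost is a table and text correction plus a short addition to section 6. The downside is that there would be no 12-month laboratory or cardiac summary table unless the tests are scheduled for all patients.

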3.8. Study procedures and visit schedule

A patient and his/her parent/parents should sign separate forms of informed consent to participation in the study before any study-related procedures.

Study procedures will be performed in accordance with the current standards of care. Procedures, evaluations and examinations not listed in the visit schedule might be performed at discretion of an attending physician in accordance with standards of medical care of the healthcare institution and patient safety requirements.

The study consists of the following stages:

- Signing of informed consent forms (separate informed consent forms for parents and the child)
- Screening
- Distribution into groups and surgery
- Early observation (24-48 postoperative hours)
- Discharge (ca. after 21 days)
- Follow-up 6 months after the operation
- Long-term follow-up – 12 months after the surgery performed

3.8.1. Procurement of informed consent from patients

The investigator should see to it that the patient's parents have received complete and adequate information on the main points of the study, its objectives, possible risks and benefits of participation verbally or in writing. The patient's parents should also be informed that they might voluntarily withdraw their child from participation in this study at any time. The patient's parents should be given the opportunity to ask questions and time for consideration.

The informed consent form signed by the patient's parents (signature of one of the parents will suffice) should be obtained before any study-related procedures.

The children who were offered to take part in the study should also be given information on the study considering their abilities to understand such information, sign and date written informed consent (a separate informed consent form) with their own hand.

The investigator should keep original informed consent forms signed by patients and their parents. Copies of the signed informed consent forms should be given to patients and their parents.

Any changes to the previously approved informed consent form during the study should be reapproved by the LEC.

3.8.2. Enrollment of patients in the study and screening

A patient is considered a study participant only after informed consent forms have been signed by a patient and their parents.

The screening visit (visit No. 1) consists of the following procedures:

- patient history;
- physical examination and clinical evaluation: physical status (body mass index);
- functional status and life quality (with VAS, FIM, MACS, GMFCS);
- Spine X-ray: scoliotic and kyphotic deformity measurements (Cobb angle), static and dynamic imbalance in frontal and sagittal planes;
- laboratory tests: clinical blood analysis, blood chemistry;
- spirometry, ECG, echocardiography;
- spine CT with the assessment of structural vertebral changes;
- MRI of the spine and spinal cord.

3.8.3. Visit No. 2. Distribution into groups and surgery

Distribution into study groups will be performed according to the results of physical examination and the evaluation of orthopedic, physical, and neurologic status and serious adverse events. Surgical correction will be performed with standard anesthesia and intraoperative safety control during deformity correction – with navigation and monitoring system, according to hospital's standards of care

3.8.4. Visit No. 3. Early observation (24-48 hours)

The following study procedures will be performed 24-48 hours after surgery (index procedure):

- Physical examination;
- Laboratory analysis: clinical blood analysis, blood chemistry;
- Evaluation of severe adverse events (if any).

3.8.5. Visit No. 4. Before discharge (ca. after 21 days)

The duration of inpatient stay is determined by standards of the healthcare institution and on the average amounts to 21 days (depending on the patient's clinical condition). The following study procedures will be performed before discharge:

- Physical examination;
- Spine X-ray: scoliotic and kyphotic deformity measurements (Cobb angle), static and dynamic imbalance in frontal and sagittal planes;
- Spine CT and verification of screw position;
- laboratory tests (clinical blood analysis, blood chemistry);
- documentation of serious adverse events.

3.8.6. Visit No. 5. 6 months after the surgery

CHILDren with neuromuscular diseases – efficacy eVALuation of spinal deformity surgeRY via different pedicle screw fixation systems study
CHIVALRY study

The following study procedures will be performed during a scheduled visit 6 months after the procedure:

- physical examination and clinical evaluation: physical status (body mass index);
- functional status and life quality (with VAS, FIM, MACS, GMFCS);
- spine X-ray: scoliotic and kyphotic deformity measurements (Cobb angle), static and dynamic imbalance in frontal and sagittal planes;
- documentation of serious adverse events.

3.8.7. Visit No. 6. 12 months after the procedure

The following study procedures will be performed during a scheduled visit 12 months after the procedure:

- physical examination and clinical evaluation: physical status (body mass index);
- functional status and life quality (with VAS, FIM, MACS, GMFCS);
- spine X-ray: scoliotic and kyphotic deformity measurements (Cobb angle), static and dynamic imbalance in frontal and sagittal planes;
- laboratory tests (clinical blood analysis) (as an option if there is a medical condition);
- spirometry, ECG, echocardiography (as an option if there is a medical condition);
- Spine CT with evaluation of screw position and fusion mass (as an option, if there are signs of a bone block in the area of instrumental fixation according to radiographs of the spine);
- documentation of serious adverse events.

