Due to the pathogenesis of neuromuscular deformity patients with such conditions have inevitable progression of spine and thorax deformity, even patients with the mature skeleton and minimal deviations (up to 20-25° by Cobb) in frontal and/or sagittal plane (Larsson E.L. et al., 2005). Early usage of rigid corset prevents significant progression at the childhood but can cause contact dermatitis and pressure ulcers. In this connection many authors insist on surgical spine stabilization at the second growth spurt (Master D.L., 2011). Patients with such conditions usually have severe and long C-type and S-type deformities with pelvic misalignment in frontal and sagittal planes. With S-type deformity body balance is often compensated, but both curves can reach 100° or more (Lonstein J., 2001). With deformity over 40° patients lose the ability to get to the vertical position and can sit only with the support. With deformity over 90° patients cannot sit (Bridwell K.H. et al., 1999; Berven S., Bradford D., 2002; Wang C.H. et al., 2007; Auerbach J.D. et al.m 2009; [name] et al., 2013). Patients in a wheelchair (III functional class by GMFCS - Gross Motor Function Classification System) have high risks of severe deformities in comparison with the bed-bound patients, due to the constant axial load (Lonstein J., 2001; Teli M. et al., 2005). Frequent reference to cardiopulmonary failure as main diagnosis in autopsy results confirms that decompensated spine deformity is the main reason for premature death of such patients (Pehrsson K., 1992; Berven S., 2002; Larsson E.L. et al., 2005; Sarwark J., 2007; Chong H.S., 2011).

Duchenne muscular dystrophy patients studies showed disease progression in all patients with deformity over 40° associated with difficulties while sitting, decrease in vital capacity, decreased performance and problems with hand movements (Hsu, 1983).

Indications for surgical correction of scoliosis in patients with NMD are progressive deformity, loss of balance while seating, back pain and discomfort (Herring JA., 2002; Labelle H, 2002; Renshaw TS, 2001). Such surgery can be performed using connector systems («growing rods») (McElroy MJ, 2011; Chandran S, 2011). The main outcome of treating scoliosis is the stabilization of respiratory parameters and increase in patient activity level (Daher YH, 1985; Brown JC, 1988; Rodillo E, 1989; Phillips DP, 1989; Bridwell KH, 1999; Larsson EL, 2005).

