3.2. Endpoints

The primary endpoint is decrease in spine deformity grade by 1 or more (according to Chaklin classification) with stabilization or improvement in lung parameters in 12 months after the surgery.

Secondary endpoints are as follows:

1. Hospitalization by all causes
2. Improvement in life quality after surgery according to scales (VAS, GMFCS, RLAS, FIM, MACS) in 6 months and 12 months after surgery.

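### The primary endpoint needs lung function at 12 months, but spirometry at that visit is done only for medical reasons, so the plan does not ensure that patients whose deformity grade improves can be scored

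*Combined protocol and SAP*

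**What the plan says.** Section 3.2 makes the primary endpoint a composite. The patient must drop at least one Chaklin deformity grade, "with stabilization or improvement in lung parameters in 12 months after the surgery". Both parts are required.

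For the 12-month visit, section 3.8.7 lists "spirometry, ECG, echocardiography (as an option if there is a medical condition". Table 1 in section 3.7 puts an asterisk on the Visit 6 spirometry mark, and its footnote reads "Performing research only for medical reasons". The same visit lists "spine X-ray: scoliotic and kyphotic deformity measurements (Cobb angle" with no condition attached.

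At screening, section 3.8.2 lists "spirometry, ECG, echocardiography" without a condition, but the spirometry row label in Table 1 carries the same asterisk. Sections 3.8.5 (discharge) and 3.8.6 (6 months) list no spirometry. Under section 3.8, examinations outside the schedule "might be performed at discretion of an attending physician in accordance with standards of medical care".

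On incomplete data, section 6 says: "Missing data will be indicated as N/A and not considered in aggregate statistics".

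**The concern.** One half of the composite is measured in everyone and the other half only in patients for whom someone sees a medical reason. A plan followed exactly can therefore leave grade responders who are neither successes nor failures.

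This matters in three ways.

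- **Evaluability depends on clinical condition.** The trigger for testing is not defined. One reading would test nearly all patients, another very few, so neither the size nor the direction of any bias can be predicted.
- **The denominator is open.** Section 6 does not say whether an untested patient with no grade decrease, who is already a known failure, stays in the summary or is dropped along with the missing spirometry value. The same data give different success rates under the two readings.
- **Nothing in the design compensates.** Section 3.3 calls the study non-comparative, so the success rate is itself the main result, and analysis cannot recover a 12-month value that was never taken. Section 1.1 states: "The main outcome of treating scoliosis is the stabilization of respiratory parameters and increase in patient activity level". The component at risk is thus one the protocol treats as central.

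**Working it through.** **Is there another source for the lung component?** The plan states no figure to reproduce, so the first step is to compare the sections.

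| Place | Spirometry | Spine X-ray |
|---|---|---|
| Screening (3.8.2) | listed without condition; Table 1 row label has the asterisk | yes |
| Discharge (3.8.5) | not listed | yes |
| 6 months (3.8.6) | not listed | yes |
| 12 months (3.8.7, Table 1) | only for medical reasons | yes |

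No other scheduled value can stand in for the 12-month one, and section 3.8 permits extra tests but does not require them.

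**Who is undetermined?** Assume that the grade is read from the 12-month X-ray and that lung parameters means spirometry. A patient with no grade decrease fails whatever the lung result. Only a grade responder without 12-month spirometry is undetermined.

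**How much could it matter?** N = 70 comes from section 1.3 (30 + 40 in section 3.3). Everything else is assumed: R = 56 grade responders (80%), 80% of tested responders with stable or improved lungs, a share f tested that is the same in responders and non-responders, no dropout, and baseline spirometry available for all.

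- Tested responders TR = round(56 × f)
- Undetermined U = 56 − TR
- Confirmed successes S = round(0.8 × TR)
- Possible success rate: S/70 to (S + U)/70, with width U/70
- Tested patients T = TR + round(14 × f)
- Reading A of section 6 (tested patients only): S/T
- Reading B (tested patients plus untested known failures): S/(70 − U)

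| f | TR | S | U | Possible rate | Width | Reading A | Reading B |
|---|---|---|---|---|---|---|---|
| 20% | 11 | 9 | 45 | 9/70 to 54/70 = 13–77% | 64 points | 9/14 = 64% | 9/25 = 36% |
| 40% | 22 | 18 | 34 | 18/70 to 52/70 = 26–74% | 49 points | 18/28 = 64% | 18/36 = 50% |
| 60% | 34 | 27 | 22 | 27/70 to 49/70 = 39–70% | 31 points | 27/42 = 64% | 27/48 = 56% |
| 80% | 45 | 36 | 11 | 36/70 to 47/70 = 51–67% | 16 points | 36/56 = 64% | 36/59 = 61% |
| 100% | 56 | 45 | 0 | 45/70 = 64% | 0 | 45/70 = 64% | 45/70 = 64% |

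The width is U/70, so it does not depend on the assumed 80% lung stability. Reading A stays at 64% only because testing is assumed to be unrelated to outcome; testing for medical reasons could move it either way.

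**Sensitivity to the number of grade responders.** With R = 49 (70%), U = 29 at 40% tested and 10 at 80% tested. With R = 63 (90%), U = 38 and 13.

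**The case against.** The strongest reply is that the data may not go missing at all. Every patient has a neuromuscular disease with a deformity needing surgery, and section 1.1 links such deformity to reduced vital capacity. A centre could find a medical reason to test almost everyone. That is possible, and it is why the claim is only that the plan does not ensure scoring. It does not remove the problem: the plan leaves testing to an undefined trigger, and if all would be tested anyway, requiring it costs almost nothing.

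Second, section 3.2 never says that lung parameters means spirometry. This stands as an assumption. It is the natural reading, because no other lung-function test is scheduled; if another measure is meant, the plan schedules none.

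Third, the figures are illustrative. No testing level in the table has more support than another, and selection by clinical condition is not modelled. Undetermined patients are also undercounted if baseline spirometry is conditional too. All of this stands. What does not depend on those assumptions is the rule that the uncertainty equals the number of undetermined patients divided by 70.

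Fourth, no test or decision threshold is attached to the primary endpoint, so no false test conclusion follows. That is right, and it limits the harm to an incomplete or selectively measured success rate. It is still the primary endpoint's rate.

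**Conclusion.** The concern holds, with high confidence, as a conflict between the endpoint in section 3.2 and the schedule in section 3.7 and section 3.8.7. Text and table agree on the condition, so it is not a slip in one place. It must be fixed, because the primary outcome is not guaranteed to be determinable in every operated patient and clinical condition decides who is evaluable.

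The amount of loss is unknown. It ranges from nothing, if all grade responders are tested, to an uninformative result if few are. This rests on the grade being read from the 12-month X-ray and on spirometry being the lung measure.

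**What to change.** 1. **Define the measure first.** Before any 12-month data are read, the sponsor names the lung parameter, sets the threshold for stabilization, and states how deaths before 12 months are counted.
2. **Schedule it.** In Table 1 and section 3.8.7, make spirometry a required outcome measurement at Visit 6 for all patients able to perform it, and record the reason when it is not done. Reconcile the asterisk on the Table 1 row label with section 3.8.2, so that a baseline value is collected for all as well.
3. **Fix the denominator in section 6.** Use all operated patients. Count no grade decrease at 12 months as failure whether or not spirometry was done. Keep as undetermined the grade responders without paired lung data, including those unable to perform the test, and patients lost or withdrawn for reasons other than death. Report the number measured, with worst-case and best-case rates.
4. **Report the parts.** Give the 12-month grade decrease separately for all patients. If testing is incomplete, do not generalise the composite beyond those tested.

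If the sponsor does not want universal spirometry, the alternative is to restate the primary endpoint so that it rests only on what is measured in everyone, with the lung outcome reported in those tested.

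The cost is low to moderate: a non-invasive test already listed at both visits, for patients who would otherwise skip it, and edits to three places. Because section 3.8 rests study procedures on standards of care, requiring the test may need ethics review. The reported rate may be lower than under the tested-only reading.

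Some loss will remain. If 5%, 10% or 20% of the 56 assumed responders cannot perform the test, U = 3, 6 or 11 and S = 42, 40 or 36. The possible rate is then 42/70 to 45/70 (60–64%), 40/70 to 46/70 (57–66%) or 36/70 to 47/70 (51–67%).
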